6.2.1 CLINICAL EXPERIENCE IN MYELOFIBROSIS WITH RUXOLITINIB

MPN-RC

A Phase II Open-label Study of Combined Ruxolitinib and Enasidenib Sinai Sinai in Patients with Accelerated/Blast-phase Myeloproliferative Neoplasm or Chronic-

phase Myelofibrosis with an IDH2 Mutation

(Myeloproliferative Neoplasms Research Consortium [MPN-RC] 119)

Ruxolitinib has been shown to produce durable clinical benefits in terms of spleen volume reduction and improvement in constitutional symptoms with an acceptable toxicity profile^{27,28}. Based on the results of two Phase III studies (COMFORT-I, COMFORT-II)^{27,28} showing improvement in spleen size, symptom control and improvement in quality of life, ruxolitinib was approved for use in patients with intermediate or high-risk myelofibrosis by the FDA. There is also evidence of a benefit in overall survival (OS) in patients treated with ruxolitinib. An OS advantage (HR=0.58; 95% CI, 0.39-0.85, p=0.005) in treated patients compared to historical controls has been reported²⁹. In addition, an analysis of the COMFORT-I study confirmed that patients treated with ruxolitinib had an OS advantage compared with placebo (HR=0.58,95%CI, 0.36-0.95, p-0.03) with a median of 102 weeks of followup³⁰. Follow-up analysis of the COMFORT-II trial has also demonstrated an OS advantage for patients treated with ruxolitinib³¹.

6.3 Enasidenib (AG-221)

MPN-RC

The IDH enzymes play critical roles in catalyzing the oxidative decarboxylation of isocitrate to produce carbon dioxide (CO2) and alpha-ketoglutarate (α -KG) enzyme in the citric acid cycle. Of the two best characterized isoforms, IDH1 and IDH2, mutations in IDH2 have been found in approximately 15% of subjects with AML^{36,37}. The mutated proteins have a gain-of-function, neomorphic activity, catalyzing the reduction of α -KG to 2-HG while lacking the ability to synthesize isocitrate³⁸. The excess accumulation of 2-HG leads to inhibition of dioxygenase dependent enzymes such as ten-eleven translocation (TET) and Jumonji which are responsible for demethylating DNA and histones, respectively, the consequence of which results in an altered epigenetic state and impaired cellular differentiation^{39,40}.

Recurring mutations in IDH2 may be important for AML pathogenesis or disease progression⁴¹. Retrospective clinical data have revealed that the presence of IDH1 mutations is associated with a worse prognosis in younger cytogenetically-normal AML subjects and subjects with IDH2 mutations had a significantly lower complete response rate³⁷. In a retrospective study of 398 subjects < 60 years of age who were diagnosed with AML and randomly assigned to receive induction therapy with high-dose or standard dose daunorubicin, IDH2 mutations were in general associated with an improved overall survival⁴². Prospective clinical studies will help further understand the impact mutations, co-mutations, and/or karyotype status have on disease outcomes in the presence of an IDH mutation.

Enasidenib is a first-in-class, selective, potent inhibitor of the neomorphic activity of IDH2 mutant enzyme and has been shown to suppress 2-HG production in enzymatic, cell-based, and in vivo systems. Pharmacology studies support that suppression of 2-HG levels by enasidenib results in alterations of cellular downstream markers, leading to a release in the block of tumor cell differentiation.

Enasidenib has rapid oral absorption, low to medium total body plasma clearance, and low to high volume of distribution. The half-lives range from 2.5 to 5.4 hours, and oral bioavailability was approximately 40% to 50% (free base) in toxicology species. Enasidenib is metabolized by multiple cytochromes (CYPs) and uridine diphosphate (UDP)-glucuronosyl transferases (UGTs). Enasidenib is a direct inhibitor for CYP2C8,2C9, 2C19 and 2D6, as well as UDP-glucuronosyl transferase 1 family, polypeptide A1 (UGT1A1). The N-dealkylated metabolite, AGI-16903 is also an inhibitor of CYP1A2, 2C8 and 2C9. Enasidenib and AGI-16903 are weak inducers of CYP3A4. Preliminary results indicate that enasidenib increased 4 β -hydroxycholesterol level in subjects, indicating CYP3A induction in patients. Enasidenib is not a substrate, but is a potent inhibitor of P-glycoprotein (P-gp) and breast cancer resistance protein (BCRP). In vitro, enasidenib is an inhibitor of organic anion transporter (OAT) 1, OATP1B1, OATP1B3, and organic cation transporter (OCT) 2, while AGI-16903 is also a substrate of P-gp and BCRP. Clinical relevance of such in vitro interactions will be evaluated in humans as needed.

The toxicity profile of enasidenib has been evaluated in repeat dose oral toxicity studies of up to 90 days in Sprague-Dawley rats, and cynomolgus monkeys and for 7 days in beagle dogs, and in the bacterial reverse mutation (Ames) and mammalian chromosomal aberration assays in vitro. Enasidenib was neither mutagenic nor clastogenic. Dose-limiting toxicities in rats after 28 days of dosing were

MPN-RC

A Phase II Open-label Study of Combined Ruxolitinib and Enasidenib Sinai

in Patients with Accelerated/Blast-phase Myeloproliferative Neoplasm or Chronicphase Myelofibrosis with an IDH2 Mutation

(Myeloproliferative Neoplasms Research Consortium [MPN-RC] 119)

multifactorial and included gastrointestinal tract atrophy and erosions, lymphoid atrophy, degeneration, and necrosis, bone marrow hypocellularity and necrosis, skeletal muscle degeneration and necrosis, pancreas and kidney epithelial vacuolation, and adrenal cortical hemorrhage and necrosis. After 90 days of dosing, non-dosing limiting target organ toxicities in rats were limited to testes/epididymides and pancreas. In monkeys, ulcerative inflammation in the large intestine was determined as the dose-limiting toxicity. No changes in cardiovascular functions were noted in monkeys; however coronary artery lesion (periarteritis) was observed at the dose associated with dose-limiting toxicity indicated above. Findings in large intestine and coronary artery in monkeys were observed following 28 days of dosing. Additional target organ toxicities secondary to decreased body weight and food consumption in monkeys included femur/tibia (either dysplasia or decreased thickness of physis), bone marrow (decreased cellularity), thymus (atrophy/involution), liver (cytoplasmic rarefaction) and pancreas (acinar cell degranulation). In dogs, there were enasidenib dose-related prolonged heart rate-corrected QT (QTc) intervals, hypotension and increased heart rate. These functional cardiovascular effects of enasidenib were the likely underlying causes of coronary artery lesions in dogs.

As of 15 Apr 2016, data are available for 330 subjects from Study AG221-C-001 who have been administered enasidenib across 13 dosing cohorts up to a 650 mg daily dose, including both BID and QD dosing regimens. Study AG221-C-002, a food effect study in healthy volunteers is complete. Study AG-221-CP-001, a pharmacokinetic (PK) and safety study in healthy male Japanese and Caucasian adult subjects, and Study AG-221-CP-002, a PK study to evaluate the metabolism and excretion and determine absolute bioavailability of enasidenib in healthy male adult subjects, are also complete. Study AG221-C-003, a Phase 1/2 dose escalation study, evaluated enasidenib at doses ≥ 100 mg daily in subjects with advanced solid tumors with an IDH2 mutation, including glioma, and in subjects with AITL with an IDH2 mutation. Doses up to 650 mg were well-tolerated. The expansion phase of AG221-C-003 was canceled based on the Sponsor's decision to focus on the relapsed refractory AML indication and not for any safety reason. Ongoing studies include a Phase 3 randomized study in subjects with R/R AML with IDH2 mutation (AG-221-AML-004), a Phase 1b/2 study in subjects with newly-diagnosed AML (AG-221-AML-005), and a Phase 1 study in subjects with newly diagnosed AML sponsored by Agios in collaboration with Celgene (AG120-221-C-001). Study AG-221-C-005 is evaluating oral AG-120 plus subcutaneous (SC) azacitidine and oral enasidenib plus SC azacitidine in subjects with newly diagnosed AML with IDH1 or IDH2 mutation, respectively, who are not candidates to receive intensive induction chemotherapy. Study AG120-221-C-001 is evaluating AG-120 or enasidenib in combination with induction and consolidation therapy in subjects with newly diagnosed AML with an IDH1 and/or IDH2 mutation.

Data from Study AG221-C-001 showed that enasidenib was well-tolerated at total daily doses up to 650 mg. The MTD was not reached in the dose escalation part of the AG221-C-001 study. Based on pharmacodynamic and efficacy data, the 100 mg daily dose was chosen for further development. No meaningful differences in nature, incidence, or severity of the Adverse Events (AE) have been observed between subjects with R/R AML, previously untreated AML, or MDS. As of 15 Apr 2016, 93 deaths have been reported in Study AG221-C-001 either on study or within 28 days of the last dose of study treatment. Deaths were attributed to complications of the underlying condition or disease progression, with an exception of 1 subject who experienced pericardial effusion complicated by fatal cardiac tamponade. Retrospective analysis of this case suggests that pericardial effusion was a likely sign of isocitrate dehydrogenase-differentiation syndrome (IDH-DS). Serious adverse events (SAEs) reported in $\geq 5\%$ of the study participants included febrile neutropenia in 79 (23.9%), pneumonia in 47 (14.2%), sepsis in 39 (11.8%), pyrexia in 28 (8.5%), leukocytosis in 27 (8.2%), IDH-DS in 24 (7.3%), lung infection in 21 (6.4%), acute renal failure in 18 (5.5%), tumor lysis syndrome (TLS) in 18 (5.5%), and fatigue in 17 (5.2%) subjects.

The safety and tolerability of enasidenib has been evaluated in more than 440 subjects enrolled in clinical studies of subjects with hematologic malignancies or solid tumors and single-dose pharmacology studies in healthy volunteers, as of the data cutoff date for this IB (15 Apr 2016 for Study AG221-C-001 and 01 Jul 2016 for all other ongoing clinical studies). In clinical studies, enasidenib overall was generally well tolerated, with a relatively low incidence of discontinuations due to AEs.

MPN-RC

A Phase II Open-label Study of Combined Ruxolitinib and Enasidenib Sinai in Patients with Accelerated/Blast-phase Myeloproliferative Neoplasm or Chronic-

phase Myelofibrosis with an IDH2 Mutation

(Myeloproliferative Neoplasms Research Consortium [MPN-RC] 119)

Specific adverse drug reactions (ADRs) to enasidenib were identified. Events of IDH-DS (similar to a syndrome observed with retinoic acid in acute promyelocytic leukemia), noninfectious leukocytosis, TLS, GI disturbances (such as nausea, diarrhea, vomiting, and associated dysgeusia and decreased appetite), and hyperbilirubinemia have been observed in subjects with hematologic malignancies. Gastrointestinal disturbances and hyperbilirubinemia have been also observed in subjects with solid tumors. IDH-DS and noninfectious leukocytosis are associated with enasidenib mechanism of action and generally decrease in incidence with time.

Preliminary analysis of PK data in Study AG221-C-001 (as of 15 Apr 2016) from subjects with advanced hematologic malignancies up to the 650 mg QD dose level demonstrated high plasma exposures, a long mean plasma half-life of enasidenib after a single dose, high drug accumulation after multiple doses, and relatively high PK variability. The mean time to Cmax (Tmax) ranged from approximately 1 to 24 hours when administered as a single dose 3 days before study treatment began. In a subset of IDH2 mutated AML subjects, correlation of drug exposure, 2-HG levels, and IDH2 mutation site was evaluated. A comparison of PK data between the 2 groups (R140Q and R172K) at the enasidenib 100-mg dose level indicated that the average steady state exposure level (AUC0-10 or Cmax) was similar. Enasidenib treatment decreased 2-HG levels in R140Q and R172K patients. Preliminary analysis showed no clear correlation between 2-HG suppression and clinical response to enasidenib.

As of 15 Apr 2016 in Study AG221-C-001, the overall response rate (ORR) (defined as complete response [CR] + CR with incomplete neutrophil recovery [CRi] + morphologic CR with incomplete platelet recovery [CRp] + partial response [PR] + marrow CR [mCR] + morphologic leukemia free state [MLFS]) among the 113 subjects in the dose escalation phase was 45.1% with a median time to first response of 1.9 months and a median time to best response of 3.7 months. Twenty-four of the 113 subjects (21.2%) achieved a best response of CR, with a median time to CR of 3.8 months. Responses occurred in all dosing groups (30 mg BID to 650 mg QD). Of the 176 subjects with R/R AML in the combined Phase 1 part of the study, the ORR was 40.3%, with a median duration of response of 5.8 months. Thirty-four of the 176 subjects (19.3%) achieved a CR, with a median duration of CR of 8.8 months. The ORR, CR, and median duration of response were similar in the subset of subjects who received the 100 mg daily dose compared with the total R/R AML population. Of the 71 responders among subjects with R/R AML, the median time to first response was 1.9 months and the median time to best response was 3.7 months. The median times to first response and best response were similar in the subset of subjects who received the 100 mg daily dose. At the time of data cutoff, median eventfree survival for subjects with R/R AML was 6.4 months (95% CI = 5.4, 7.5) and median overall survival was 9.3 months (95% CI = 8.2, 10.9).

This study⁴³ led to the Food and Drug Administration approval to enasidenib for the treatment of adult patients with relapsed or refractory acute myeloid leukemia with IDH2 mutation in August 2017.

Please refer to the current version of the enasidenib IB for detailed information concerning the available pharmacology, toxicology, drug metabolism, clinical studies, and AE profiles of enasidenib.

7. STUDY OBJECTIVES

Ruxolitinib (also known as INCB018424), a JAK1/2 inhibitor, and enasidenib (AG-221, an IDH2 inhibitor) are effective and tolerable treatments for patients with myelofibrosis (MF) and acute myeloid leukemia (AML), respectively. We hypothesize that the combination of these agents in patients with MPN with an IDH2 mutation will improve the overall clinical response to therapy without causing excessive toxicity.

7.1 PRIMARY OBJECTIVES

• To estimate the efficacy of ruxolitinib and enasidenib combination therapy in patients with accelerated-phase and blast-phase disease. Efficacy will be defined as the proportion of patients who achieve a best leukemia response of: complete response (CR), Partial Response (PR),

in Patients with Accelerated/Blast-phase Myeloproliferative Neoplasm or Chronicphase Myelofibrosis with an IDH2 Mutation

(Myeloproliferative Neoplasms Research Consortium [MPN-RC] 119)

complete response with incomplete recovery of counts (Cri), as assessed by the modified 2013 International Working Group (IWG) Response Criteria.

7.2 SECONDARY OBJECTIVES

- To assess the efficacy of the combination of ruxolitinib with enasidenib in patients with accelerated-phase and blast-phase disease using complete (CBR) and partial blast response (PBR).
- To assess the efficacy (CR, PR, Clinical Improvement) of the combination of ruxolitinib with enasidenib in patients with PMF, post-PV MF, or post-ET MF in chronic phase and 4-9% blasts as assessed by the modified 2013 International Working Group (IWG) Response Criteria
- To determine the safety of the combination of ruxolitinib and enasidenib based on the Common Terminology Criteria for Adverse Events version 5.0 (CTCAE).
- To assess the impact of the combination of ruxolitinib with enasidenib on the overall survival of advanced phase MPN patients.

7.3 EXPLORATORY OBJECTIVES

- To determine the impact of the combination of ruxolitinib with enasidenib in patients with PMF, post-PV MF, or post-ET MF, on patient quality of life as assessed by the Myelofibrosis Symptom Assessment Form (MF-SAFv4.0).
- To evaluate the pharmacodynamics of ruxolitinib and enasidenib when combined in this population.
- To evaluate the effects of combined therapy on gene expression and global methylation status.
- To explore changes in mutant allele burden and clonal architecture of disease.

8.0 PATIENT ELIGIBILITY

Eligibility waivers are not permitted. Subjects must meet all of the inclusion and not meet any of the exclusion criteria to be registered to the study by the Central Office. Study treatment may not begin until a subject is registered.

8.1 INCLUSION CRITERIA

- 1. Willing and able to adhere to the study visit schedule and all protocol requirements
- 2. Subjects must be \geq 18 years at the time of signing the Informed Consent Form (ICF).
- 3. Diagnosis of:
- a. Accelerated-phase (≥ 10% blasts in PB or BM) or blast-phase (≥ 20% blasts in PB or BM) myeloproliferative neoplasm (with history of prior myelofibrosis, polycythemia vera, or essential thrombocythemia)
 - b. Previously treated patients with myelofibrosis with persistent disease or progressive disease (persistent or progressive splenomegaly, leukocytosis, anemia, or thrombocytopenia) with intermediate-1 or greater risk disease according to 2013 International Working Group (IWG) criteria, and 4-9% circulating blasts.
- 4. Demonstration of an IDH2 mutation.
- 5. Platelet count \geq 75,000 X 10⁹/L for chronic phase myelofibrosis patients.
- 6. Prior therapy with either ruxolitinib or enasidenib is permitted, but not a combination of ruxolitinib and enasidenib.
- 7. Patients with chronic phase myelofibrosis on ruxolitinib must be on the drug for at least 3 months and on a stable dose for at least one month.

in Patients with Accelerated/Blast-phase Myeloproliferative Neoplasm or Chronicphase Myelofibrosis with an IDH2 Mutation

(Myeloproliferative Neoplasms Research Consortium [MPN-RC] 119)

- 8. Subjects must have an Eastern Cooperative Oncology Group (ECOG) performance status of 0 to 2. ECOG 3 status will be allowed if attributable to MPN.
- 9. Patients must have adequate organ function as demonstrated by the following:
 - a. Direct bilirubin ≤ 2.0 mg/dL, unless due to Gilbert's disease or current elevations in direct bilirubin associated with existing enasidenib use.
 - b. Serum creatinine< 2.0 mg/dL.

MPN-RC

- c. ALT and AST \leq 3x upper limit of normal (unless transaminitis is considered to be related to MF).
- 10. Females of childbearing potential (FCBP) must have a negative serum or urine pregnancy test with a sensitivity of at least 50 mIU/mL within 10 14 days prior to starting enasidenib and must either commit to continued abstinence from heterosexual intercourse or begin TWO acceptable methods of birth control, one highly effective method and one additional effective method AT THE SAME TIME, at least 4 weeks before she starts taking enasidenib. FCBP must also agree to ongoing pregnancy testing. Men must agree to use a condom during sexual contact with a female of child bearing potential even if they have had a successful vasectomy. All patients must be counseled at a minimum of every 28 days about pregnancy precautions and risks of fetal exposure.
- 11. All study participants must be able to swallow oral medication.

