The choice of appropriate treatment options for MF patients is currently based on the prognosis of the individual patient⁸. Several prognostic scoring systems that utilize various clinical parameters including age, leukocyte count, hemoglobin level, platelet count, monocyte count, peripheral blast count, presence of splenomegaly, constitutional symptoms and degree of bone marrow fibrosis (BMF) are helpful in predicting patient outcome^{4,9-11}. Patients under the age of 65 without significant co-morbidities and intermediate/high risk disease by Lille classification or int-2/high risk by IWG-MRT PSS are considered candidates for reduced intensity conditioning stem cell transplant (RIC-SCT). Allogeneic stem cell transplant is the only modality that offers the potential for cure, although the risk of transplant related mortality (TRM) and the morbidity and mortality associated with graft versus host disease (GVHD) are considerable¹². Patients older than 65 or with competing co-morbidities are considered not to be candidates for RIC-ASCT but rather candidates for therapies such as interferon-alfa, immunomodulatory agents (IMiDs) JAK2-TKIs or histone deacetylase inhibitors (HDACI). MF patients that either fail current experimental therapies or are ineligible due to limiting cytopenias often have no alternative treatment options other than agents including hydroxyurea, melphalan, thalidomide, lenalidomide and danazol that achieve response rates of 20-50%, but have not been shown to alter the natural progression of disease^{13,14}.

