10. TREATMENT DOSAGE AND ADMINISTRATION

Patients who are on ruxolitinib will continue their current dose. Patients who are not on ruxolitinib will receive ruxolitinib per Table 1 dosing based on platelet count (modified package insert dosing). Enasidenib will be given at 100 mg daily on enrollment for patients with accelerated and blast phase myelofibrosis regardless of platelet count (this will be deemed Cycle 1). Patients with chronic phase myelofibrosis will receive Enasidenib at starting dose of 50 mg daily for cycle 1. The dose of Enasidenib will be increased to 100 mg for cycle 2 if the platelet count stays above 50,000 at the end of cycle 1 (Table 3a) and no other therapy emergent SAE of grade \geq 2 developed (except grade 2 hyperbilirubinemia that is acceptable for dose escalation).

Ruxolitinib and enasidenib will be given orally in an outpatient setting unless the patient is being seen inpatient for another reason. Ruxolitinib and enasidenib will be given orally in 28-day cycles.

Patients should fast 2 hours before and 1-hour post enasidenib. Ruxolitinib may be administered independent of fasting and may be given with enasidenib. All protocol mandated visits will be performed at one of the participating institutions. Patients will return to the treating institution at a minimum of weekly during Cycles 1 and 2, every 4 weeks for Cycles 3 and beyond. Additional clinic visits will be mandated according to the patient clinical condition and at the discretion of the treating provider. Patients will have an end of study visit for a safety follow-up at 30 days after their last dose of therapy.

The dosages of ruxolitinib and/or enasidenib can be reduced, based on assessment of adverse events, if any occur, as described below in Section 10.1. Missed or vomited doses of ruxolitinib or enasidenib will not be made up.

Twenty-eight days is considered one cycle of therapy. Attempts will be made to provide an adequate treatment period with the combination of at least 6 cycles, unless significant toxicity is observed, to account for delayed time to response observed with biologic agents. Responders will continue therapy indefinitely unless progression of disease occurs, toxicity warranting discontinuation of therapy is

A Phase II Open-label Study of Combined Ruxolitinib and Enasidenib Sinai in Patients with Accelerated/Blast-phase Myeloproliferative Neoplasm or Chronic-

phase Myelofibrosis with an IDH2 Mutation

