 - If Grade 4 (QTcF> 500 msec or > 60 msec change from baseline with torsade de pointes or polymorphic ventricular tachycardia or signs/symptoms of serious arrhythmia), subjects should be admitted to hospital when QTc prolongation is first observed for continuous cardiac monitoring and be discharged only after review by a cardiologist. Dosing with enasidenib should be permanently discontinued.

10.1.2ABNORMAL LEVEL OF LIVER ENZYMES(HYPERBILIRUBINEMIA)

Subjects with elevations in $ALT \ge 3$ -fold ULN, subjects will be monitored using the algorithm:

- Repeat LFT (i.e., ALT, AST, total bilirubin, ALP, GGT) within < 3 days of the initial test. Follow-up 2-3 times weekly, and weekly when stable.
- Perform additional diagnostic follow up:
 - Focused medical history, including review of prior history of liver or biliary disorders, concurrent symptoms, review of all concomitant medications (e.g., acetaminophen-containing medications, over-the-counter or herbal medications, nutritional supplements) including any changes in medications, detailed review of alcohol use.
 - Hepatitis serology (anti-HAV, HBsAg, anti-HBs, anti-HB core, anti-HCV, HCV RNA, EBV and CMV screen), and autoantibodies (e.g., ANA, anti-smooth muscle antibody).
 - Complete physical examination.
 - Liver ultrasound and follow-up imaging as appropriate.
 - Additional evaluation as appropriate (INR, PT).

Hyperbilirubinemia generally decreased in frequency as enasidenib treatment continued. $\$

in Patients with Accelerated/Blast-phase Myeloproliferative Neoplasm or Chronicphase Myelofibrosis with an IDH2 Mutation

(Myeloproliferative Neoplasms Research Consortium [MPN-RC] 119)

 Table 1. Ruxolitinib initial dose for patients' baseline platelet count by cohort*

Cohort	Plt>100 X10 ⁹ /L	Plt 50-100 X10 ⁹ /L	Plt 20-50 X10 ⁹ /L	Plt<20 X10 ⁹ /L
Blast/Accelerated Phase	20 BID	15 BID	10 BID	5 BID
Chronic Phase	15 BID	10 BID**	NA	NA

*Patients already receiving Ruxolitinib will begin trial at the dose they were on prior to combination therapy. **Chronic phase patients with platelet<75 will not be enrolled to the trial.

Table 2a. Ruxolitinib Dose Adjustment for patients with accelerated and blast phase MF for NON-HEMATOLOGICAL AEs*

Dose level	PATIENTS' BASELINE PLATELET COUNTS			
	Plt>100 X10 ⁹ /L	Plt 50-100 X10 ⁹ /L	Plt 20-50 X10 ⁹ /L	Plt<20 X10 ⁹ /L
+1	25 BID	20 BID	NA	NA
0	20 BID	15 BID	10 BID	5 BID
-1	15 BID	10 BID	5 BID	5QD
-2	10 BID	5 BID	5 QD	Stop treatment
-3	5 BID	5 QD	Stop treatment	

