-4	5 QD	Stop treatment		
-5	Stop treatment			

* For patients with accelerated and blast phase MF, treatment will continue at the same dose regardless of platelet count.

Table 2b. Ruxolitinib Dose Adjustment for patients with chronic phase MF for thrombocytopenia or nonhematological AEs

Dos	e level	DOSE ADJUSTMENT FOR THROMBOCYTOPENIA		
		Plt>100 X10 ⁹ /L	Plt 50-100 X10 ⁹ /L	Plt 20-50 X10 ⁹ /L
	+1	20 BID	15 BID	N/A
DOSE ADJUSTMENT FOR NON- HEMATOLOGICAL AES	15 BID	10 BID	5 BID*	
	-1	10 BID	5 BID	5 QD
	-2	5 BID	5 QD	Stop treatment
	-3	5 QD	Stop treatment	
	-4	Stop treatment		

MPN-RC

A Phase II Open-label Study of Combined Ruxolitinib and Enasidenib Sinai in Patients with Accelerated/Blast-phase Myeloproliferative Neoplasm or Chronic-

phase Myelofibrosis with an IDH2 Mutation

(Myeloproliferative Neoplasms Research Consortium [MPN-RC] 119)

 Table 3a. Enasidenib Dose Adjustment for thrombocytopenia

MF chronic phase Cycle 1	MF chronic phase Cycle 2 and above	MF chronic phase Cycle 2 and above	MF chronic phase Cycle 2 and above	MF accelerated phase and blast phase
Platelet >75X10 ⁹ /L	Platelet > 50X10 ⁹ /L	Platelet 35-50X10 ⁹ /L	Platelet<35X10 ⁹ /L	Any platelet count
50mg	100mg	50mg	Hold	100mg

Table 3b. Enasidenib Dose Adjustment for non-hematological AE

Dose Level	Enasidenib
-1	50 mg QD
0	100 mg QD

MPN-RC

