	PR: ≥50% reduction in abnormal metaphases
	(partial response applies only to patients with at least ten abnormal metaphases at baseline)
Molecular remission	Molecular response evaluation must be analyzed in peripheral blood granulocytes and
	requires confirmation by repeat testing within 6 months window
	CR: Eradication of a pre-existing abnormality
	PR: ≥50% decrease in allele burden
	(partial response applies only to patients with at least 20% mutant allele burden at baseline)
Cytogenetic/molecular relapse	Re-emergence of a pre-existing cytogenetic or molecular abnormality that is confirmed by repeat testing

EMH, extramedullary hematopoiesis (no evidence of EMH implies the absence of pathology- or imaging study-proven nonhepatosplenic EMH); LCM, left costal margin; UNL, upper normal limit

*Baseline and posttreatment bone marrow slides are to be interpreted at one sitting by a central review process. Cytogenetic and molecular responses are not required for CR assignment.

+Grading of MF is according to the European classification

Thiele et al. European consensus on grading bone marrow fibrosis and assessment of cellularity. Haematologica, 2005;90:1128.

It is underscored that the consensus definition of a CR bone marrow is to be used only in those patients in which all other criteria are met, including resolution of leukoerythroblastosis It should also be noted that it was a particularly difficult task for the working group to reach a consensus regarding what represents a complete histologic remission

#Immature myeloid cells constitute blasts + promyelocytes + myelocytes + metamyelocytes + nucleated red blood cells. In splenectomized patients, <5% immature myeloid cells is allowed.

§See above for definitions of anemia response, spleen response, and progressive disease. Increase in severity of anemia constitutes the occurrence of new transfusion dependency or a >20 g/L decrease in hemoglobin level from pretreatment baseline that lasts for at least 12 weeks. Increase in severity of thrombocytopenia or neutropenia is defined as a 2-grade decline, from pretreatment baseline, in platelet count or absolute neutrophil count, according to the Common Terminology Criteria for Adverse Events (CTCAE) version 4.0. In addition, assignment to CI requires a minimum platelet count of ≥25 000 × 10(9)/L and absolute neutrophil count of ≥0.5 × 10(9)/L

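### The chronic-phase platelet minimum is 1000 times the figure in Tables 1 and 3a, the platelet floor for clinical improvement conflicts with the CR range, and the entry risk class cites criteria that contain no risk classes

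*Combined protocol and SAP*

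**What the plan says.** **Entry platelet count.** Inclusion 5, in the Study Summary (Section 4) and again in Section 8.1, requires at least "75,000 X 10⁹/L for chronic phase myelofibrosis patients". Table 1, whose columns are in units of 10⁹/L, carries the footnote "Chronic phase patients with platelet<75 will not be enrolled to the trial". Table 3a heads its chronic-phase cycle 1 column "Platelet >75X10", followed by the exponent 9 per litre. Section 8.0 adds: "Eligibility waivers are not permitted".

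**Platelet floor for CI.** Appendix A defers to the 2013 IWG-MRT and ELN criteria for CI. The Appendix B footnote to those criteria states that "assignment to CI requires a minimum platelet count of ≥25 000 × 10(9)/L". In the same appendix, CR needs platelets of at least 100 × 10⁹/L and below the upper normal limit. One route to PR accepts 50 to below 100 × 10⁹/L.

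**Risk class.** Inclusion 3b, also in both Sections 4 and 8.1, admits previously treated myelofibrosis "with intermediate-1 or greater risk disease according to 2013 International Working Group (IWG) criteria". The background (Section 6.1) speaks of several prognostic scoring systems. It mentions the Lille classification and says that patients who are "int-2/high risk by IWG-MRT PSS are considered candidates" for transplant.

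**Where these enter the analysis.** Section 20.2 defines chronic-phase response as CI+PR+CR within 6 cycles. It takes at least 1 response in 9 evaluable patients as a sign of activity, with 90% power at a true rate of 25%. Section 22.1 divides responders by treated eligible patients.

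**The concern.** These are operative thresholds. Two decide who may enter the chronic-phase cohort, and one decides whether a patient counts as a responder in it.

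Registration requires every inclusion criterion to be met (Section 8.0) and is not completed otherwise (Section 14.2.1). Taken at face value, inclusion 5 leaves the chronic-phase cohort with no eligible patient and the Section 22.1 denominator empty.

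The CI floor bears on the response count. If CI cannot be assigned, the cohort's endpoint reduces to CR+PR. The Study Schema (Section 3) and Section 27 also tie continuation after cycle 6 to response, and for chronic-phase patients response includes CI.

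Inclusion 3b is a different kind of fault. A class called intermediate-1 has to come from a prognostic score, and the criterion points to a document that, as reproduced here, is not one.

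**Working it through.** **1. The plan's own figure.** The Gehan power in Section 20.2 is P(at least 1 response in n) = 1 − (1 − p)ⁿ.
- n = 9, p = 0.25: 1 − 0.75⁹ = 0.925.
- n = 8, p = 0.25: 1 − 0.75⁸ = 0.8999, just short of 0.90.

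So 9 is the smallest n that reaches 90%. The stated sample size reproduces, with the 90% read as a minimum.

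**2. Entry platelet count.**
- Inclusion 5: 75,000 × 10⁹/L, which is 75,000,000 per microlitre.
- Table 1 footnote and Table 3a: 75 × 10⁹/L, which is 75,000 per microlitre.
- Ratio: 75,000 / 75 = 1000.

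The likely origin is visible in the text. Section 10 writes another threshold as a bare count, "if the platelet count stays above 50,000 at the end of cycle 1", and Table 3a gives that same threshold as 50 × 10⁹/L. Two unit styles are in use, and inclusion 5 combines the number of one with the suffix of the other.

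**3. CI floor.**
- Appendix B footnote: 25,000 × 10⁹/L, which is 25,000,000 per microlitre.
- Against the lower CR limit: 25,000 / 100 = 250 times.
- Against the lower limit of the second PR route: 25,000 / 50 = 500 times.

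CR must also stay below the upper normal limit. The appendix gives no number for that limit, but any value below 25,000 × 10⁹/L puts the floor for the lesser response above the whole permitted range for the greater one. The same footnote sets the CI neutrophil floor at 0.5 × 10⁹/L, half the CR minimum of 1 × 10⁹/L. That ordering is the expected one; the platelet part alone breaks it.

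**4. What losing CI would do to the chronic-phase rule.** The documents give no chronic-phase CR+PR rate, so the rates here are assumed. With n = 9 and only CR and PR counting:

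| Assumed CR+PR rate | P(at least 1 response in 9) |
|---|---|
| 10% | 1 − 0.90⁹ = 0.61 |
| 5% | 1 − 0.95⁹ = 0.37 |
| 2% | 1 − 0.98⁹ = 0.17 |

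The planned value is 0.925 at a 25% rate.

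**5. Risk class.** No arithmetic applies. Sections 7.1, 7.2, 20.1 and 22.2 and Appendix A all use the 2013 IWG label for response criteria. Appendix B lists response, stable disease, progression, relapse and remission categories and no risk groups. The one IWG risk tool named is the IWG-MRT prognostic system in Section 6.1, which carries no 2013 date there and is not cited in 3b.

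**The case against.** The strongest reply is that the entry figure is an editorial slip which the protocol itself resolves. The Table 1 footnote and Table 3a both show the unit, and no site could apply the literal number. This largely stands. A reader might infer that the trial can enrol no chronic-phase patient; that follows only from the literal wording. What remains is that a binding criterion, stated twice, contradicts two tables, with no waiver available.

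A reader might also infer that the CI floor is wrong by the same factor of 1000. The documents do not support that figure, because they give no second value for CI. The conflict with the CR range can be shown; the size of the slip cannot. Nor can one tell from the documents whether the number was carried over from the published criteria. Either way it is this protocol's operative text.

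On 3b, one might infer that sites will choose different scores and classify the same patient differently. This is not shown. The wording is criteria, not response criteria; patients are registered by the Central Office (Section 8.0); and the sponsor reviews eligibility before enrolment (Section 15). The documents give no example of a patient whose eligibility would turn on the score. The point is a citation mismatch.

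Finally, the chronic-phase cohort is descriptive and its response is a secondary endpoint (Section 13.2). That is correct and limits the consequence.

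**Conclusion.** The point holds within limits.

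- **Inclusion 5** is 1000 times the figure in Tables 1 and 3a. The contradiction is certain, and the tables make the intended unit recoverable.
- **The CI floor** cannot be reconciled with the CR range in the same appendix, so CI could not be assigned as written. This assumes only that the upper normal platelet limit is below 25,000 × 10⁹/L. A unit slip is the likely explanation, but it is an inference.
- **Inclusion 3b** cites a source which, as used in this protocol, has no risk classes. The intended score cannot be established from the documents.

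The reach is the chronic-phase cohort: 9 evaluable patients, at most 10 enrolled, and the CI part of CI+PR+CR. Its CR and PR definitions have attainable platelet limits of their own, and the sample size of 9 does not change. The accelerated/blast-phase primary endpoint (CR+PR+CRi) and its Simon design are untouched, so none of this supports a claim that the main result is at risk. The probabilities of 0.61, 0.37 and 0.17 illustrate a literal application under assumed rates; they do not predict what will happen.

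**What to change.** Five text edits:

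- **Inclusion 5, Sections 4 and 8.1 (two edits):** reconcile the platelet figure with the units of Tables 1 and 3a. The sponsor confirms the value.
- **Appendix B, CI footnote (one edit):** the sponsor checks the platelet floor against its source and corrects the unit. No value is proposed here, since the documents hold no second figure.
- **Inclusion 3b, Sections 4 and 8.1 (two edits):** replace the 2013 IWG reference with the prognostic score the sponsor intended. It should have an intermediate-1 class and apply to primary, post-PV and post-ET myelofibrosis. The IWG-MRT system mentioned in Section 6.1 should not be adopted by default, because the corresponding entry in the reference list is titled for primary myelofibrosis.

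No design figure, sample size or analysis method changes. The cost is small but not nil: the edits need an amendment, and Sections 25.4 and 26.5 require IRB approval before it takes effect.
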